The trans-theoretical model proposes that motivation to change develops over a series of stages (pre-contemplation, contemplation, preparation, action, maintenance) and that facilitating change requires stage-specific interventions (Prochaska & DiClemente 1984; Prochaska 1984). At the earliest stages, people are not committed to change and intervention focuses on instilling motivation. In the IMR program, motivational interviewing (Corrigan et al. 2001; Miller & Rollnick 2002) is used at the beginning and throughout the program to help clients develop their own vision of recovery, to identify and pursue their personal goals based on that vision, and to explore how improved illness management can help them achieve these goals.

The stress-vulnerability model (Liberman et al. 1986; Zubin & Spring 1977) posits that the course and outcome of schizophrenia is determined by the dynamic interplay of biological vulnerability, stress, and coping. IMR is aimed at interrupting the cycle of stress and vulnerability that leads to relapse and poor functioning (see figure 1). In IMR, the proximal goal is to teach clients the fundamentals of illness self-management based on the stress-vulnerability model (ie, adherence to medications, reduced substance use, increased social support, increased coping, involvement in meaningful activities) in order to improve illness outcomes such as symptoms, relapses, and hospitalizations. Then, through the combination of pursuing personal goals and improved illness self-management, the distal goal of IMR is to help clients make progress toward recovery, including objective (e.g. community functioning, social relationships, work) and subjective (e.g. sense of purpose, hope, confidence) dimensions."

Conceptual Framework for the Illness Management and Recovery program

[figure not shown]

Figure 1 source: (Mueser et al. 2006)

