1.2 Relevance

1.2.1 Strengthening demand-orientation

What are the main elements of IMR?

Illness Management and Recovery (IMR) is a program of care in the form of a training course for patients with severe and persistent psychiatric problems, based on a combination of different types of interventions focused on recovery. The idea underlying the training course is that the patient learns to gain control of his illness (illness management) and to make appropriate choices based on accurate information and skills training.

IMR can be described as a structured training program for people with severe and persistent mental illness which helps to:

- Set meaningful personal goals
- To gather information and acquire skills to achieve a greater degree of control over the psychiatric illness.
- To work on recovery.

IMR is based on a review of controlled research (Mueser et al 2002a) in which five types of interventions (Mueser et al call them 'strategies') emerged which were incorporated into the training program.

These include psycho-education, cognitive behavioral approaches to improve medication compliance (medication management), relapse prevention by developing a crisis plan, strengthening social support with training in social skills and training to learn skills to cope with persistent symptoms (coping skills training).

To motivate patients to learn how to deal better with their disease and to make progress in their lives, IMR begins with an exploration of the meaning of recovery for the patient and the setting of personal recovery goals that can be worked on during the training course. The program includes 11 modules (see 6. Intervention).

It is intended that patients follow all modules. The total duration of the training program is on average one year, but the duration varies, depending on the frequency of sessions and the number of sessions per module. IMR may be offered individually or in a group format.

The importance of recovery

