1.2.3 Scientific significance

The research may contribute to answering the question whether IMR can be called an EBP. In the RCT by Hasson-Ohayon et al. (2007) IMR participants showed significant improvements in knowledge about their illness and showed progress towards their personal goals compared to patients with care as usual (CAU). Scores of clinicians showed a significant improvement in 'overall outcome'. Both the IMR- as the CAU group showed a significant improvement in coping and neither group showed change in social support.

In the RCT by Levitt et al (2009), executed in supported housing the intervention group scored significantly better in illness management and clearly had fewer symptoms and better psychosocial functioning.

In the RCT by Färdig et al (2011), the IMR-participants showed better illness management, less symptoms, better psychosocial functioning.

An effective factor in IMR in groups could be peer support (see Castelein et al, 2008a and 2008b and Castelein 2009), for which also indications come forward in our pilot study.

Nevertheless, in the field of psychiatric research in the Netherlands there still are doubts about the evidence-based status of IMR. There has not yet been done a RCT on IMR in the Netherlands. IMR is not yet mentioned in the multidisciplinary guidelines on Schizophrenia in the Netherlands (see 1.1).

Transfer of knowledge

IMR and the scientific status of IMR have a growing interest in the Netherlands and abroad. The results of the study are thus of significance for many people and will be studied by many. The results of our study will be transferred by newsletters, conferences and articles in scientific journals.

2. Objective

The aim of this study is to examine the effectiveness of the IMR program compared to care as usual (CAU) in patients with SMI.

3. Research questions

Research questions are:

What are the effects of "IMR + CAU", compared to "CAU only" on:

- 1. Illness management, as experienced by clients (primary outcome measure)
- 2. Recovery.

The hypotheses are that "IMR + CAU", (IMR offered in group format), compared to "CAU only" leads to:

1. Better Illness Management:

(Better scores on IMR-scales, less symptoms and relapses, better medication adherence, less alcohol & drugs use, more insight into their own problems, more social and coping skills, more social support).

2. Better recovery:

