The Service Engagement Scale (Tait et al. 2002) is a 14-item measure consisting of statements that assess client engagement with services, which case managers rate on a four-point Likert scale from 'not at all or rarely' to 'most of the time'. The total score ranges from a minimum of zero to a maximum of 42. Higher scores indicate lower engagement. Four sub-scales assess availability ('when a visit is arranged, the client is available'), collaboration ('the client actively participates in managing his/her illness'), help-seeking ('The client seeks help to prevent a crisis') and treatment adherence ('The client refuses to cooperate with treatment'). The scale has high internal consistency and retest reliability, including discrimination between criterion groups, in an assertive outreach team (Tait et al, 2002).

Insight into own problems: Insight Scale (IS, 8 self-report items) (PI-scale) (Birchwood et al, 1994). This 8-item self-report scale was designed to be sensitive to changes in levels of insight, and captures three dimensions of insight: perceived need for treatment, awareness of illness and relabeling of symptoms as pathological. Higher scores indicate greater levels of insight. The psychometric properties of the scale are called excellent (Tait et al. 2003).

Symptoms: The Brief Symptom Inventory (BSI) (53 items) (Derogatis & Melisaratos 1983; Derogatis 1993; De Beurs, 2008). The BSI instrument (self-report scale) provides an overview of a patient's symptoms and their intensity at a specific point in time and can be used to measure patient progress during and after treatment to monitor change. The BSI test is brief and requires 8-10 minutes to complete, making it well-suited for repeated administrations over time to evaluate patient progress. The authors report good internal consistency reliability for the nine dimensions , ranging from .71 on Psychoticism to .85 on Depression. Test-retest reliability for the nine symptom mensions ranges from .68 (Somatization) to .91 (Phobic Anxiety), and for the three Global Indices from .87 (PSDI) to .90 (GSI). Studies attesting to the validity of the BSI are found in the manual (Derogatis, 1993).

Relapses: The number of relapses (operationalized in the number of hospital admissions) during and after participating in the IMR-training will be compared with the number of relapses in the year before participating in IMR.

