8.2.4. Research data

Data on primary, secondary and tertiary outcome measures and the mediating factors will be collected at baseline (before randomization), after the IMR-training (from 9 to 12 months) and during follow-up (after 15 - 18 months). The interviewers will be blind for the (experimental or control) condition of the patient. For the recruitment of participants and data collection, students will be employed.

During the first contact (at baseline) and after the patient has given informed consent, the research interview will take place and the interviews will be conducted. Subsequently randomization will take place. Each assessment will last up to 80 minutes. If desired, the interview will take place on two occasions. The assessments will be done at the location where the patient usually comes. Besides the previously mentioned outcome measures and mediating factors at baseline the following data will also be collected:

- Demographic data: age, sex, living situation, source of income, education level, country of birth of the patient and of his father and his mother.

- Consumption of mental health care: number of outpatient contacts, number of crisis contacts, number of admissions and the number of compulsory admission orders (total and in the last two years) during the past two years before and after moment of measurement 1.
- Psychiatric diagnosis: DSM-IV-TR diagnosis (five axes) according to the clinician. We realize that this is not always reliable, but it is not possible with the resources available to do a standardized diagnostic interview.

The analysis will be based on the intention to treat principle. Data will be collected of patients who drop out of the IMR program. Based on the pilot study, during the IMR intervention, 50 % drop out from IMR is expected. In order to do analyses related to generalizability of the study, the demographic characteristics of all patients who refused to participate will be registered, as well as the characteristics of the patients who drop-out from the study.

The demographic variables, consumption of mental health care and psychiatric illness will be collected by the researcher from the administration of the institution, supplemented by data from the file.

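### Relapse is measured only by hospital admissions and compared with the year before IMR, so the result can support a claim about admissions but not the hypothesis of fewer relapses than under CAU

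*Protocol*

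**What the plan says.** Section 3 of the protocol (Research questions) predicts, for IMR + CAU against CAU only: "Better scores on IMR-scales, less symptoms and relapses, better medication adherence". Relapse is thus one named component of hypothesis 1, and the hypothesis is a contrast between arms.

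Section 8.1.2, part a, gives the only definition of relapse: "The number of relapses (operationalized in the number of hospital admissions"). The count covers the time during and after IMR and "will be compared with the number of relapses in the year before participating in IMR". No symptom criterion, crisis contact or clinical judgement enters the definition.

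Four other places bear on it:

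- Section 1.1 (Theoretical base of IMR) adopts a quoted model in which self-management is taught "in order to improve illness outcomes such as symptoms, relapses, and hospitalizations". Relapses and hospitalizations are two items in that list.
- Section 1.2.1 describes one ingredient of IMR as "relapse prevention by developing a crisis plan".
- Section 8.2.4 collects "number of outpatient contacts, number of crisis contacts, number of admissions and the number of compulsory admission orders", before and after the first measurement. Section 8.1.2, part c, uses crisis contacts and admissions for the cost analysis.
- Section 9 plans linear mixed models with group comparisons for the secondary outcomes.

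**The concern.** Two features of one sentence separate the measure from the hypothesis.

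First, all participants are outpatients, so a relapse handled by crisis contact counts as no relapse. If this loss were equal in both arms, it would mainly cost sensitivity. It may not be equal, because the protocol describes IMR as affecting how patients use services. Patients develop a crisis plan and learn to find suitable care (section 1.2.1), module 10 deals with getting needs met in the mental health system (section 6), and the IMR arm is expected to use less CAU (section 8.2.4). Fewer admissions would be reported as fewer relapses even if relapse frequency had not changed. A real fall in relapses managed without admission would be missed.

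Second, the stated comparison is with each IMR participant's own preceding year. That does not test IMR + CAU against CAU only, the year before IMR is undefined for a CAU patient, and the two periods differ in length.

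**Working it through.** **1. The definition against the hypothesis.** Section 3 concerns relapses between arms. Section 8.1.2 counts admissions, before against after. Section 1.1 lists relapses and admissions as separate outcomes. Neither half of the 8.1.2 sentence matches the hypothesis it serves.

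**2. The comparison windows.** Section 4 gives a mean training time of 12.6 months in the pilot and a follow-up measurement 6 months later.

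- During plus after IMR: 12.6 + 6 = 18.6 months. Prior period: 12 months. Ratio 18.6 / 12 = 1.55.
- With the 15 to 18 months given in section 8.2.4: 15 / 12 = 1.25 to 18 / 12 = 1.50.
- CAU arm (section 4): 12 + 6 = 18 months. Between arms: 18.6 / 18 = 1.03.

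If raw counts were compared, an unchanged admission rate would show 1.25 to 1.55 times as many admissions after the start of IMR as before. The protocol does not say whether counts or rates are meant.

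**3. How far a shift in place of care could mislead.** The protocol states no relapse rate, admission rate or power for this outcome, so there is no figure of its own to reproduce. The following is an illustration. From the protocol: 111 IMR and 74 CAU patients at follow-up (section 8.2.1), about 1.5 years, alpha 0.05 (taken as two-sided). Assumed: the same relapse rate r in both arms, 0.4 or 0.8 per year; probability a that a relapse leads to admission, CAU v IMR, of 0.40 v 0.30, 0.40 v 0.25 or 0.50 v 0.30; overdispersion φ of 1.0 or 1.5.

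Expected admissions: m = n × 1.5 × r × a. Standard error of the log rate ratio: SE = √[φ(1/m₁ + 1/m₀)]. Rejection probability: Φ(|ln RR|/SE − 1.96) plus the small opposite tail. The true relapse rate ratio is 1.0 throughout.

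| IMR arm affected | Case | a, CAU v IMR | r | φ | m₁, m₀ | Admission rate ratio | SE | Rejection |
|---|---|---|---|---|---|---|---|---|
| All | lowest | 0.40 v 0.30 | 0.4 | 1.5 | 19.98, 17.76 | 0.75 | 0.399 | 11% |
| All | highest | 0.50 v 0.30 | 0.8 | 1.0 | 39.96, 44.40 | 0.60 | 0.218 | 65% |
| Half | lowest | 0.40 v 0.35 | 0.4 | 1.5 | 23.31, 17.76 | 0.875 | 0.386 | 6% |
| Half | highest | 0.50 v 0.40 | 0.8 | 1.0 | 53.28, 44.40 | 0.80 | 0.203 | 20% |

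For the second row: ln 0.60 = −0.511; 0.511 / 0.218 = 2.34; Φ(2.34 − 1.96) = 0.65.

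The half-affected rows average the two values of a, for example (0.30 + 0.50) / 2 = 0.40. One half is the completion share expected in section 8.2.1: 60 / 120 = 50%.

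**The case against.** The protocol presents the crisis plan as relapse prevention. It nowhere says that the plan moves care out of hospital, and it gives no figure for such an effect. That stands: the shift is plausible but not shown. A reader might infer that IMR lowers admissions without preventing any relapse; the document does not support that.

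The proxy is declared in the same sentence as the outcome, the outcome is secondary, and admissions come from institutional records, which limits rating bias when clinicians are unblinded. This also stands, so it would go too far to say that admissions carry no evidence on relapse. They are indirect evidence. BSI symptom scores can be read beside them, but these describe single points in time at three assessments and can miss an episode between visits.

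The upper range in the illustration needs every IMR patient to be affected for the whole period. With half affected it falls to 6% to 20%, close to the nominal 5% at the low end. None of these figures estimates this trial's error rate.

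A combined count of admissions or crisis contacts might seem the natural repair. It is not clearly better. IMR may prompt patients to seek help early, which could raise crisis contacts while relapses fall. Counting once per episode would also need dates and a linking rule, which the protocol does not describe.

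**Conclusion.** The point holds as a mismatch between measure and claim. As planned, any fall in admissions would be called a fall in relapses, and a change in where relapses are managed could not be told apart from a change in how often they occur. How large that confusion might be is unknown; the 6% to 65% range rests wholly on assumed rates, an assumed shift and the share of the arm affected.

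The mismatch in the comparison is firmer, because it needs no assumption about IMR's effect. Section 8.1.2 sets IMR patients against their own prior year, while sections 3 and 9 call for a contrast with CAU. The 1.25 to 1.55 imbalance in window length matters only if raw counts are used.

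This touches one component of a secondary hypothesis. It does not affect the primary outcome, the patient version of the IMR-scale, or the sample size.

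**What to change.** - In section 8.1.2 and in hypothesis 1, name the outcome hospital admissions and limit the conclusion to admissions.
- Replace the comparison with the preceding year by a comparison between arms: the admission rate over the same length of follow-up in both arms, adjusted for admissions in the year before baseline. Section 8.2.4 already plans admission data before and after the first measurement.
- Report the rate of crisis contacts between arms separately beside it, so that fewer admissions accompanied by more crisis contacts would be visible as a possible shift in place of care.
- Do not make a combined admission-or-crisis-contact count the test of the relapse claim.

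The cost is a narrower secondary claim, a change of wording in two places and one extra descriptive comparison. Admissions and crisis contacts are already collected, so no new assessment is needed.

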8.1.3. Exploratory analysis

The pilot study showed that women significantly more often are IMR completers and that completers at baseline scored better on the IMR-scales and on the GAF (psychosocial functioning). This makes it interesting to examine whether women benefit more from IMR than men and whether patients who at baseline score higher in terms of illness management, psychosocial functioning and symptoms, improve more than patients who at baseline score lower on these domains. Earlier IMR research was often focused on patients with psychotic disorders. We want to investigate whether the effect varies by diagnosis group. We are able to explore this because in the IMR-training of Bavo Europoort chronic patients with various diagnoses participate. Since half of the population of outpatients of Bavo Europoort has an immigrant background, we would like to explore whether IMR for participants from ethnic minorities is as effective as for participants of native background.

8.2 Procedures

8.2.1 Selection of patients

It is assumed that we need to screen approximately 687 patients for participation in the study. An estimated 515 patients (80%) will meet all inclusion criteria and will be asked by the clinicians to participate in the study. It is expected that about 40% of these patients are willing to participate in the study and then we get the amount we need (n = 200). Patients will be randomized in a ratio of 3:2. After drawing lots there will be 120 patients in the IMR-condition and 80 in the control condition.

We expect that in the IMR condition 37% will drop-out of IMR in the phase between randomisation and the inflow into the (individual) Module 1 and in the phase from module 1 to the inflow in the IMR group (module 2). We expect that in the IMR-condition there will approximately 78 patients who start the IMR- training groups. Based on the results of the pilot study it is expected that 77 % (n = 60) of these people will complete the IMR groups.

Drop out of the IMR-program does not mean dropping out of the study (see in 8.2.4 the intention-to-treat principle). We expect that of the 120 patients in the experimental condition, that in the second moment of measurement score at least 115 patients can be measured, and at follow-up measurements at least 111 patients. We expect that of the 80 patients in the control condition that in the second moment of measurement score at least 77 patients can be measured and at follow-up measurements at least 74 patients (See Annex 1, flowchart of randomisation). We expect this dropout of the study is only 8% because patients who want to withdraw from care will not wish to participate in IMR.

8.2.2 Training of clinicians

Clinicians treating patients with severe and persistent psychiatric illnesses of BavoEuropoort will be involved in the research.

IMR group leaders have received an IMR-group leader-training of two days about the main aspects of IMR given by two experienced instructors of BavoEuropoort and they will all receive two-weekly supervision.

8.2.3 Recruitment of patients

First, the investigator will provide information to the team leaders of the aforementioned outpatient teams and ask for their participation in the study.

Three months before starting the randomization the clinicians of the six participating teams will receive the information about the study from the researcher followed by information on the process of randomization. During a treatment team meeting, the investigator will explain the research plan. Subsequently, the files of the aforementioned patients will be screened for the inclusion criteria.

After screening the files on the inclusion criteria potential participants will receive an information letter from their clinician and will be asked whether they accept that the researcher contacts them. The researcher will then contact the patient, explain the research project and ask for written informed consent.

If a patient refuses to participate he/she will be asked for permission to use demographic and diagnostic data in order to determine the generalizability of the sample. After signing the informed consent, the first measurement will take place, followed by the randomization.

8.2.4. Research data

Data on primary, secondary and tertiary outcome measures and the mediating factors will be collected at baseline (before randomization), after the IMR-training (from 9 to 12 months) and during follow-up (after 15 - 18 months). The interviewers will be blind for the (experimental or control) condition of the patient. For the recruitment of participants and data collection, students will be employed.

During the first contact (at baseline) and after the patient has given informed consent, the research interview will take place and the interviews will be conducted. Subsequently randomization will take place. Each assessment will last up to 80 minutes. If desired, the interview will take place on two occasions. The assessments will be done at the location where the patient usually comes. Besides the previously mentioned outcome measures and mediating factors at baseline the following data will also be collected:

- Demographic data: age, sex, living situation, source of income, education level, country of birth of the patient and of his father and his mother.

- Consumption of mental health care: number of outpatient contacts, number of crisis contacts, number of admissions and the number of compulsory admission orders (total and in the last two years) during the past two years before and after moment of measurement 1.
- Psychiatric diagnosis: DSM-IV-TR diagnosis (five axes) according to the clinician. We realize that this is not always reliable, but it is not possible with the resources available to do a standardized diagnostic interview.

The analysis will be based on the intention to treat principle. Data will be collected of patients who drop out of the IMR program. Based on the pilot study, during the IMR intervention, 50 % drop out from IMR is expected. In order to do analyses related to generalizability of the study, the demographic characteristics of all patients who refused to participate will be registered, as well as the characteristics of the patients who drop-out from the study.

The demographic variables, consumption of mental health care and psychiatric illness will be collected by the researcher from the administration of the institution, supplemented by data from the file.

The researcher can not be blind for the (experimental or control) condition of the patient. Number, duration and nature of all treatments which people get in both conditions are recorded. We expect that in the "IMR + CAU"-condition the patient will use less CAU than in the 'CAU only'-condition.

In addition, we will examine exploratory the mechanisms behind a (possible) effect of IMR as well as the experiences with IMR in practice.

The application of the questionnaires may last in total one hour. At the first interview patients receive an amount of \in 20, -, at the moment of measurement of the final-scores \in 25, and at follow-up measurements \in 30, - as a sign of appreciation for participation in the study.

The research data will be stored and reported in an anonymous manner. Personal data are coded. The research team has access to the key of the code.

